# **IRB Minimal Risk Protocol Template**

Note: If this study establishes a human specimen repository (biobank) for research purposes, do not use this template. Use the Mayo Clinic Human Specimen Repository Protocol Template found on the IRB home page under Forms and Procedures at http://intranet.mayo.edu/charlie/irb/

First-time Use: Use this template to describe your study for a new IRB submission.

- 1. Complete the questions that apply to your study.
- 2. Save an electronic copy of this protocol for future revisions.
- 3. When completing your IRBe application, you will be asked to upload this document to the protocol section.

**Modification:** To modify this document after your study has been approved:

- 1. Open your study in IRBe. Click on the study 'Documents' tab and select the most recent version of the protocol. Save it to your files.
- 2. Open the saved document and activate "Track Changes".
- 3. Revise the protocol template to reflect the modification points, save the template to your files
- 4. Create an IRBe Modification for the study and upload the revised protocol template.

#### **Research Question and Aims**

## Hypothesis:

It is hypothesized that the ADI CPM Monitoring System (test device) will be able to measure:

- a) Respiration rate and relative changes in tidal volume in healthy human volunteers with enough accuracy and precision to validate the intended use of the system.
- b) Thoracic impedance with enough precision and consistency with respect to reference measurements to validate the intended use of the system.

## **Objectives:**

Primary Objectives

1) Validate Respiration Rate (RR) accuracy derived by the Cardiopulmonary Management (CPM) System in the range of 6-40 BPM\*

- 2) Validate relative changes in tidal volume (rTV) derived by the CPM System\*
- 3) Validate consistency in measurement-to-measurement and day-to-day changes in median Thoracic Impedance (TI) as well as position-dependent Delta Impedance ( $\Delta Z$ ) derived by the CPM System

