## **Outcome Measures:**

Primary Outcome Measures

- 1) Accuracy of CPM System calculated RR versus reference device\*
  - Correlation coefficient between reference and test device
  - RMSE accuracy
- 2) Accuracy of CPM System calculated rTV as compared to reference device calculated TV\*
  - Correlation coefficient between reference device and test device within subjects
  - Average correlation coefficients across subjects for rTV for immediate and long timeframes between measurements
- 3) Standard deviation of the difference between reference measured impedance and CPM measured impedance across multiple measurements
- 4) Average of within-subject standard deviation (STD) of TI values from test device for short term measurements

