## **Study Duration:** *Healthy Cohort*

The duration per participant will be one supervised session of approximately two hours. At least one safety follow-up call will occur within one week of the in-clinic session.

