## Pathologic Cohort

The duration per participant will be two supervised sessions of approximately one hour each. These two study sessions will take place within one day and will be separated by at least one hour. At least one safety follow-up call will occur within one week of the in-clinic session.

It is expected that the entire study duration, from the enrollment of the first participant to the completion of the final participant's site visit, will be approximately 12 weeks total, with 6 weeks allotted per cohort.

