## Pathologic Cohort

Patients will be recruited and begin the study as they are identified and consent to the study. Recruiting will end when 20 patients have initiated the study. One participant will participate in the study at a time, with the duration of each of two visits lasting approximately one hour (the total commitment for any given participant being approximately 2 hours spread over the course of one day).

Upon arrival to the clinic on the day of the study visit, prior to the application of the reference and test devices, skin inspection of the application site will be conducted. The reference bioimpedance device will be placed on the participant and a reference measurement will be taken. These electrodes will be worn for the entire duration of the study, even between visits, in order to ensure placement consistency, although reference and test impedance measurements will never be taken concurrently and reference measurements will never be taken with the CPM Device on the participant to avoid device interference. The reference bioimpedance device

electrodes will be placed within 2 cm from the CPM Device's electrode placement on the left chest of the participant. After disconnecting the reference device from the electrodes, the CPM Device will then be applied to the participant's chest as described in the IFU materials supplied with the device (the study team will also have received training on the proper placement of the device prior to the initiation of the study). A skin marker will be used to mark around the device in order to later place it in the exact same location. On the CRF, the time that the CPM Device is placed on the chest for the first time will be denoted.

A Baseline measurement will then be taken using the CPM Mobile Application in order to assign a systemgenerated patient ID to the participant as well as to establish the tilt angle for the following measurements. The measurement should proceed with two positions; the first half of the measurement should be in a sitting-upright "Fowler" position, and the second half should be in a lying-flat "Supine" position.

In reference to the table below, subjects will be instrumented with the ADI device and laboratory-based reference impedance device along with a mouthpiece connected to a pneumotachometer and gas analyzer (only for the last three measurement items). In addition, they will be instrumented with an ECG for the indicated items.

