\*\*Measurements with the CPM Device refer to one entire reading of the CPM System, which takes approximately 2 to 3 minutes and includes both sitting and lying down in each measurement.

Readings will not be considered "successful" or "complete" unless all CPM device errors are resolved prior to the device streaming mode. In the case that a contact or tilt error cannot be resolved, the measurement must be repeated until the data quality is deemed sufficient. If the device begins peeling away from the skin during a measurement (as noted by a participant) and the streaming data quality looks questionable, the measurement must be repeated. The IFU can be followed for troubleshooting tips regarding issue with data quality. The device may have to be replaced, the skin moisturized, or the adhesive on the device replaced. Adhesives will be replaced between each placement of the test device. Any note regarding measurement issues and steps taken to resolve these issues must be noted in the CRF.

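### Primary Objective 3 promises validation of day-to-day thoracic impedance changes, but no subject is measured on a second day

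*Combined protocol and SAP*

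**What the plan says.** Objectives, Primary Objectives item 3: "Validate consistency in measurement-to-measurement and day-to-day changes in median Thoracic Impedance (TI". The same sentence covers delta impedance between body positions.

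Outcome Measures lists two primary impedance measures. Item 3 is "Standard deviation of the difference between reference measured impedance and CPM measured impedance across multiple measurements". Item 4 is "Average of within-subject standard deviation (STD) of TI values from test device for short term measurements". Neither mentions days.

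Study Duration gives the healthy cohort a single visit: "The duration per participant will be one supervised session of approximately two hours". For the pathologic cohort it says: "These two study sessions will take place within one day and will be separated by at least one hour". Study Procedures, Pathologic Cohort, repeats this: "the total commitment for any given participant being approximately 2 hours spread over the course of one day". The only planned contact after the visit day is a safety call.

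The Endpoints list under Pathologic Cohort Data Analysis sets two thoracic impedance limits: a within-subject SD below 6 ohms from one measurement to the next (short term), and an SD relative to the reference of at most 6 ohms for both short- and long-term measurements. The available text gives no interval for long term. Thoracic Impedance Endpoint Justification derives the 6 ohm limit from a change of 4 ohms over 5 days.

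**The concern.** A primary objective names a property that the design has no means of observing. The study is meant to ready the system for a 510(k) submission (Study Design), and the Background gives daily transmission of measurements to the care team as the product's end goal. Day-to-day stability is thus close to what a reader would want to know. If both impedance endpoints are met, the objective as worded lets the result be taken as validation of day-to-day consistency when no such data exist. The 5-day rationale for the limit makes that reading more natural.

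**Working it through.** The core of this is a comparison of the objective with the schedule.

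**Days of data per subject**
- Healthy cohort: one session, so 1 calendar day.
- Pathologic cohort: two sessions on one day, so 1 calendar day.
- Between-day intervals per subject: 1 − 1 = 0 in each cohort.

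**What the pathologic schedule does contain** (Study Procedures table)
- CPM readings: one baseline (item 2), then three labelled applications of three measurements each, 3 × 3 = 9 labelled measurements.
- Six of the nine (Applications 1 and 2) come before the one-hour break and three (Application 3) after it.
- Reference impedance readings: items 1, 3, 7 and 12, so three before the break and one after.
- Reference readings are never taken with the CPM device on, so the device comes off and goes back on between applications. The text adds: "Adhesives will be replaced between each placement of the test device". The site is held fixed: "A skin marker will be used to mark around the device in order to later place it in the exact same location". The reference electrodes stay on between the sessions.

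The data can therefore describe three things: repeat measurements within one application, re-application within a session (Application 1 versus 2), and re-application after a gap of at least one hour on the same day (Applications 1 and 2 versus 3). Anything that differs only between days is outside them.

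**Time scale behind the limit**
- Endpoint justification: 2 kg × 2 ohms/kg = 4 ohms, then spread over 5 days, which is 5 × 24 = 120 hours.
- Longest comparison in the study: within one day, with a minimum gap of 1 hour.

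**Would more subjects help?** The plan's own figure is reproduced by ((1.96 + 1.65) × 5.1 / 6)² = (3.61 × 0.85)² = 9.42, rounded up to 10, with 20 planned. That arithmetic is not at fault. With one day per subject, between-day variation within a subject cannot be estimated at 10, 20 or any other number.

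**The case against.** The strongest reply is that day-to-day is loose wording in one sentence. Hypothesis (b) speaks only of precision and consistency with respect to the reference, the outcome measures and endpoints do not mention days, and the one-day schedule is stated openly in two places. Success is decided by the endpoints. No passage announces a day-to-day claim in the submission, so the harm depends on how a reader takes the objective. This stands as an argument about severity. It does not remove the mismatch: part of a primary objective has no outcome measure and no data.

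A second reply is that re-application is a fair proxy for repeated use. In part it is, since the device is removed and replaced with new adhesives. But the site is marked, the reference electrodes stay on, and nothing specific to another day can enter.

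A third concerns the term long term. Study-activity figures are missing from the available text, so a definition there cannot be excluded, and the table offers a workable reading through its one-hour break. This part is therefore a request for clarity, not a shown error. The one-day design does not depend on it.

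A reader might also go further and combine the 5.1 ohm SD in the pathologic Sample Size Justification with the 6 ohm limit, to infer how little between-day variation the device can afford, or that it would fail across days. The documents do not support that. The 5.1 ohms has no stated period, so it may or may not already include variation over days. It is described as the SD of thoracic impedance in an individual, whereas the long-term limit applies to the SD relative to the reference. No between-day value is given anywhere.

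**Conclusion.** The objective is wrong as written: it claims validation of day-to-day changes, and the study yields zero between-day comparisons per subject in either cohort. Both impedance endpoints can be met with that part untested. The conclusion rests only on the stated schedule and needs no assumed figure.

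Severity is moderate. The remedy changes the wording of the objective, the endpoint and the claim; no limit, sample size or visit has to change. The finding does not say that between-day precision is poor, that the 6 ohm limit is wrong, or that the same-day data lack value. A pass would support same-day repeatability and re-application with controlled placement.

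**What to change.** Text changes:

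1. Reword Objective 3 to within-day measurement-to-measurement and re-application consistency of median thoracic impedance and delta impedance, with placement controlled by skin marking. Delta impedance has no limit of its own in the Endpoints list, and rewording alone does not give it one.
2. In the pathologic Endpoints, assign the items of the Study Procedures table. For example: short term is the three measurements within one application; same-session re-application is Application 1 versus 2; long term is Applications 1 and 2 versus Application 3, after the gap of at least one hour. Say also whether the baseline reading (item 2) counts.
3. State that a pass supports same-day repeatability and re-application only, not day-to-day consistency or 5-day trend detection.

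This needs no extra visit or subject. The cost is a narrower primary claim for the submission.

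If the sponsor wants to keep the day-to-day claim, data from a second day are needed. Moving the existing second session to another day is one option. It adds no session but does add a second attendance, and Application 1 versus 2 would still give same-day re-application. The CPM-minus-reference difference should be analysed by day, because a raw between-day SD would mix device error with real fluid change. The plan must also say how the reference electrodes are handled, since they now stay on between sessions and re-placing them would add reference error to the difference. With 20 subjects and one between-day change each, the SD of that change has 19 degrees of freedom. Assuming normality, its 95% interval runs from √(19/32.85) = 0.76 to √(19/8.91) = 1.46 times the estimate.

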## Secondary Objectives\*\*

1) Confirm the accuracy of the skin temperature and ECG capabilities of the CPM System

## **Outcome Measures:**

Primary Outcome Measures

- 1) Accuracy of CPM System calculated RR versus reference device\*
  - Correlation coefficient between reference and test device
  - RMSE accuracy
- 2) Accuracy of CPM System calculated rTV as compared to reference device calculated TV\*
  - Correlation coefficient between reference device and test device within subjects
  - Average correlation coefficients across subjects for rTV for immediate and long timeframes between measurements
- 3) Standard deviation of the difference between reference measured impedance and CPM measured impedance across multiple measurements
- 4) Average of within-subject standard deviation (STD) of TI values from test device for short term measurements

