## *Thoracic Impedance and Delta Impedance Derivation:*

The CPM System collects impedance spectroscopy at a variety of frequencies in two positions (usually Supine and Fowler/sitting upright).

The magnitude of thoracic impedance, at 100kHz excitation frequency, is computed as the median of impedance in each body position. The impedance is derived from two different body positions and is displayed as Thoracic impedance (median of impedance in the position with lower tilt) and the change in thoracic impedance (the difference between those two positions, reported as " $\Delta Z$ ").

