The exercises below will then be followed, with the time of the start of each exercise recorded in the CRF. Each exercise will last approximately 2 minutes, or the time that it takes to complete one full measurement with the CPM device in measurement mode (initiated by the CPM mobile app). Reference bioimpedance will be denoted at the beginning of each measurement in both a sitting and laying down position, following the CPM Device measurement flow. All CPM Device measurements include both a Fowler and a Supine portion.

Participants will be asked to breathe normally throughout the course of all measurements, including during the final three measurements which include the use of a device that tracks respiration rate and tidal volume. Reference devices to measure skin temperature and ECG will also be used during clinic visit two, before and after the CPM Device usage.

Subjects are to be instrumented with both the ADI device and reference impedance, mouthpiece, pneumotach, sampling line for O2 and CO2, ECG, and skin temperature.

Item	Description	Device/Mode	Duration	
1	Baseline reference TI measurement*	Bioimpedance reference	1 min	
2	Baseline measurement	CPM/Baseline Setup, App	3 min	
3	Reference TI measurement	Bioimpedance reference	1 min	
4	Application 1/Measurement 1**	CPM/Patient, App	2 min	
5	Application 1/Measurement 2	CPM/Patient, App	2 min	
6	Application 1/Measurement 3	CPM/Patient, App	2 min	
7	Reference TI measurement	Bioimpedance reference	1 min	
8	Application 2/Measurement 1	CPM/Patient, App	2 min	
9	Application 2/Measurement 2	CPM/Patient, App	2 min	
10	Application 2/Measurement 3	CPM/Patient, App	2 min	
t = 1 hour				
11	Reference skin temperature, ECG data	Reference temperature, ECG devices	1 min	

12	Reference TI measurement	Bioimpedance Reference	1 min
13	Application 3/Measurement 1; RR/TV	Reference spirometer, CPM/Patient,	2 min
	measurement	Арр	
14	Application 3/Measurement 2; RR/TV	Reference spirometer, CPM/Patient,	2 min
	measurement	Арр	
15	Application 3/Measurement 3; RR/TV	Reference spirometer, CPM/Patient,	2 min
	measurement	Арр	
16	Reference skin temperature, ECG data	Reference temperature, ECG devices	1 min

\* Measurements with the bioimpedance reference device refer to the length of time that it takes to get a stable thoracic impedance reading in both a sitting and lying down position.

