# Endpoints

Thoracic Impedance Precision (primary)

- Std < 6 Ohms from measurement to measurement (short term) within a subject
- Std of Z to reference  $X \le 6$  Ohms for short- and long-term measurements
- Respiration Rate Accuracy (secondary)
- RMSE < 2 bpm between reference and test device
- *Tidal Volume Accuracy (secondary)* 
  - $R^2$  value > 0.5

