# **Thoracic Impedance Endpoint Justification**

To determine the required precision for an impedance monitor to detect trends of worsening cardiopulmonary conditions, we looked into clinical standards. The ESC guidelines for the diagnosis and treatment of  $HF^1$  recommend that patients with an unexpected weight gain of >2kg in 3 days should increase their diuretic or alert their healthcare team. Using this as the guide for the change to be detected, we looked into the corresponding impedance change per kg of weight gain in patients with cardiopulmonary conditions. Gudmundsson *et al.* reported a change of 2.3 kg and 4.8 ohms (~2.1 ohms/kg) in the weeks preceding a major HF event. Note that those changes were reported using an implantable device which might be different from the thoracic impedance measured by the CPM system. Early data collected by the CPM project team show that an increase in 1kg corresponds to a 2.32 ohms decrease in the thoracic impedance. For the purpose of estimating the required precision, we will assume a 20hms/kg change.

If we define an event per the ESC guideline for weight changes, (>2kg/3days), and using the conversion factor above, we get a change of 4 ohms in 3 days. In order to estimate the precision needed for the CPM system, we assume an even slower change of 4 ohms in 5 days. In order to detect a change of 4 ohms over 5 days for a patient with a known baseline, the required precision is 6.1ohms. We will set the desired precision for the CPM system at 6ohms.

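### Averaging within-subject SDs taken from a few readings makes the short-term impedance SD read about 3% to 11% low against its 6 ohm limit

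*Combined protocol and SAP*

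**What the plan says.** Item 4 of the primary Outcome Measures is the "Average of within-subject standard deviation (STD) of TI values from test device for short term measurements". The Endpoints section for the pathologic cohort sets the criterion as "Std < 6 Ohms from measurement to measurement (short term) within a subject". A second primary criterion limits the SD of CPM impedance relative to the reference to 6 "Ohms for short- and long-term measurements".

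The Thoracic Impedance Endpoint Justification explains the limit. To detect a 4 ohm change over 5 days, "the required precision is 6.1ohms", and this is set at 6. That calculation uses 2 ohms/kg, although the section also cites about 2.1 ohms/kg from an implantable-device study and the sponsor's early data, in which 1 kg "corresponds to a 2.32 ohms decrease in the thoracic impedance".

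Each CPM measurement yields one TI value, the "median of impedance in the position with lower tilt". The Study Procedures table schedules a baseline CPM measurement, three measurements in each of applications 1 and 2 (the last is "Application 2/Measurement 3"), and three more in application 3 after the one-hour gap. A reference reading precedes each application, and "reference measurements will never be taken with the CPM Device on the participant", so the applications are separate placements.

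The plan does not state which readings count as short term, how many enter each subject's SD, or whether the 6 ohm limit applies to the average or to every subject. It gives no pooled-variance estimator, small-sample correction or confidence limit for this outcome.

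**The concern.** The sample variance is unbiased, but its square root is not: with few readings the sample SD falls below the true SD on average. More subjects make the average more stable around the wrong value, so enrolling 20 rather than the calculated 10 does not help.

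Two things follow. The figure reported as the device's short-term precision, in a study meant to support a 510(k) submission, is too small at every true SD. And if the limit applies to the average, the criterion is more lenient than the 6 ohms the plan justifies, by an amount that depends on an unstated number of readings.

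**Working it through.** **Inputs.** Limit 6 ohms (Endpoints). Planning SD 5.1 ohms and 20 subjects (Sample Size Justification, pathologic cohort). Readings per SD, k, are not stated. The procedures table allows k = 3 (one application), 6 (both visit-1 applications), 7 (those six plus the baseline) or 9 (all three applications).

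**The plan's own figure.** n = ((1.96 + 1.65) × 5.1 / 6)² = 9.42, rounded up to 10. This reproduces the stated n = 10, which is not affected by the point made here.

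**Bias.** For k independent normal readings with true SD σ, the expected sample SD is c4(k)·σ, where c4(k) = √(2/(k−1)) · Γ(k/2) / Γ((k−1)/2). The true SD that averages to exactly 6 is 6/c4(k).

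| k | c4 | Shortfall | True SD averaging to 6 | Expected average SD at a true 5.1 |
|---|---|---|---|---|
| 3 | 0.8862 | 11.4% | 6.77 | 4.52 |
| 6 | 0.9515 | 4.8% | 6.31 | 4.85 |
| 7 | 0.9594 | 4.1% | 6.25 | 4.89 |
| 9 | 0.9693 | 3.1% | 6.19 | 4.94 |

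If true SDs also differ between subjects with an assumed coefficient of variation (CV) of 20–30%, the shortfall below the root-mean-square SD is 1 − c4/√(1 + CV²): 13–15%, 7–9%, 6–8% and 5–7% for k = 3, 6, 7 and 9.

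**Chance of passing this criterion alone** (20 subjects, limit on the across-subject summary). The average-SD rule was simulated. The pooled rule is exact: P(χ² with 20(k−1) df < 36·20(k−1)/σ²). Entries are average SD / pooled SD.

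| True SD | k = 3 | k = 6 | k = 7 | k = 9 |
|---|---|---|---|---|
| 5.1 | 99.6% / 94.6% | 99.9% / 99.3% | >99.9% / 99.7% | >99.9% / 99.9% |
| 6.0 | 86% / 53% | 76% / 52% | 74% / 52% | 71% / 51% |
| 6.5 | 65% / 27% | 34% / 15% | 28.5% / 12% | 20% / 9% |

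**If every subject had to be below 6.** At a true 5.1, P(χ² with k−1 df < 36(k−1)/5.1²) raised to the power 20 gives 0.3%, 0.6%, 0.8% and 1.2%. A device at its planning value would almost always fail, so this reading is hardly workable. Item 4, the only definition of the statistic, says average.

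**Slack in the limit.** If required precision scales with the ohms/kg factor (an assumption), 6.1 × 2.1/2 = 6.4 and 6.1 × 2.32/2 = 7.1. Only the 3-reading break-even of 6.77 exceeds 6.4, and none exceeds 7.1.

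**If two applications count as short term.** Let MSW be the mean square within application and MSB the mean square between applications within subject. The six-reading variance is (4·MSW + MSB)/5, whereas the total variance is estimated without bias by (2·MSW + MSB)/3. Take assumed SDs of 5 within and 4 between applications, so the total is √(25 + 16) = 6.40. Simulated averages are:

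- average of six-reading SDs: 5.54
- within-application pooling: 4.98
- root-mean-square of the six-reading SDs: 5.86
- √((2·MSW + MSB)/3): 6.37

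**The case against.** The strongest objection is that the leniency is computed for one criterion in isolation. Suppose the second primary criterion must also be met and its SD is taken once over all nine CPM-minus-reference differences in all subjects, with a noise-free reference and no between-subject offset. A true 6.5 ohm device then passes both only about 7% of the time whichever k is used, and pooling lowers that by only 1 to 2 points. This stands as a reason to call the effect modest. It does not settle the matter, because the plan neither says both must pass nor how the second SD is formed. If that SD is also averaged per subject, the joint pass rate at 6.5 is about 17–20%. In neither case is the figure reported for outcome 4 corrected.

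The other objections also carry some weight:

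- **Planning value.** The plan gives 5.1 as a maximum, and there the choice of estimator hardly changes the outcome. But the plan itself concedes that this estimate comes from a small sample in a different population.
- **Noise.** With 20 subjects the standard error of the average SD is 10.4%, 6.9% and 5.5% of σ for k = 3, 6 and 9, so the bias is at most about one standard error. Unlike noise, it always runs in the same direction.
- **Threshold.** The 6 ohm limit has slack from rounding the conversion factor. That slack is not a documented allowance for estimator bias.
- **Range.** The 3% end requires readings taken after the one-hour gap to count as short term. With visit 1 only, the shortfall is 4.8%, or 4.1% with the baseline included.

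**Conclusion.** The point holds. As defined, outcome 4 understates short-term SD by 3.1% to 11.4%, so a true 6.19 to 6.77 ohms averages out at the limit. These sizes assume independent normal readings, equal true SDs across subjects, and 9 down to 3 readings per SD. The spread reflects the plan's own silence on which readings are short term. Unequal SDs make the shortfall larger.

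The leniency also assumes that the limit applies to the average. The effect on pass or fail matters mainly for a device at or just above 6 ohms and is small at 5.1. The plan should be changed, but this alone does not put the study's conclusion in doubt.

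**What to change.** 1. State which readings form each subject's short-term SD, and that the 6 ohm limit applies to the across-subject summary.
2. Replace the average of SDs with the square root of the mean within-subject variance over that set, and compare it with 6 ohms.
3. If both visit-1 applications count as short term, do not pool within application only. Use √((2·MSW + MSB)/3). It needs no further data, is unbiased for the total variance before the square root is taken, and cannot be negative.

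**Cost.** One formula in the analysis plan, with no new data or subjects. With independent readings the reported SD rises by about 3% (9 readings) to 13% (3 readings), or by 5% to 18% if subjects' SDs differ with a CV of 20–30%. At a total SD of 5.1, the chance of passing this criterion falls from 99.6% to 94.6% with 3 readings. With 6 independent readings it falls from 99.9% to 99.3% (root-mean-square) or 99.0% (two mean squares). With the two-mean-squares form it is about 98% if the 5.1 splits into 4.5 within and 2.4 between applications, and 94.8% if the variance splits equally (both splits assumed). The loss is about 5 points at most in these scenarios.

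This corrects the estimate only. It adds no confidence bound, so a device at exactly 6 ohms would still pass about half the time.
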